## **13.3** Demographics and Baseline Characteristics

Age, sex, height, weight medical history and other baseline characteristics will be collected at Screening. Continuous variables will be summarized using descriptive statistics; categorical variables will be summarized using counts and percentages.

## 13.4 Method for the Analysis of Primary Effectiveness Parameter

The primary effectiveness analysis will be based on Healing at twenty-four (24) months for Treatment Complete Cohort.

The proportion of subjects with healing, along with the exact 95% confidence interval, will be provided for healing at 24 months.

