## 2.3 Healing Rates for Traditional Root Canal Therapy

While the literature presents many different definitions of healing, any future endodontic clinical studies should utilize a healing endpoint based upon both clinical and radiographic findings. The radiographic finding should be based upon the periapical index score, with PAI 1 or 2 indicating success. Additionally, no clinical signs or symptoms should be present. Separating complete healing and incomplete healing will also more clearly present study results.

Success rates over time varied widely across the literature. Generally, most healing had occurred 1 year following root canal treatment, though healing was shown to take up to 4 years or more. Thus, success rates should also be presented at each time-point studied and not just a cumulative number over a range of follow-up periods. An approximate success rate for 1 year follow-up would be 68-70% while that success rate would increase to 80-85% after four years.

While effective chemomechanical canal preparation is extremely important, the literature indicated other factors significantly affected long-term prognosis for the patient. If a patient presented with apical periodontitis and had a periapical lesion, the long-term success was significantly lower. Thus, including a large number of patients with a pre-operative periapical radiolucency could result in lower long-term success rates. Effective obturation to within 2 mm within the radiographic apex and effective coronal restorations also improved long-term success. The number of roots treated and mid-treatment complications could also impact success rates. These facts highlight the importance of choosing the appropriate patient

population and standardizing the treatment regimen in clinical studies so that the variable being studied can be reliably assessed.

While a number of studies have been published regarding the healing and success rates following root canal treatment, the quality of this literature is generally less than other medical disciplines. A dearth of randomized, controlled trials exists in endodontic research, and a large number of retrospective studies are published. Finally, the lack of standardization of study design and clinical endpoints across studies makes the comparison of results between studies difficult at best. *(See Appendix I. Healing Literature Report)* 

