#### 3.0 STUDY PURPOSE AND OBJECTIVES

The purpose of this study is to assess healing rates and post-procedure pain following root canal therapy with the Sonendo GentleWave System as compared to a literature control.

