#### **3.1** Primary Effectiveness Endpoints

Subject teeth in the Treatment Complete cohort that are healed or are healing at the twentyfour month Follow-up Visit.

Healed is defined by absence of a radiographic indication of apical periodontitis (PAI <3) and absence of clinical signs and symptoms.

Healing is defined by a reduction of radiolucency (if radiolucency is present at Baseline) and/or reduction of clinical signs and symptoms (if clinical signs and symptoms are present at Baseline)

Secondary analysis will be performed after all Treatment Complete subjects have completed the 12 month Follow-up Visit.

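### Section 13.4 bases the primary analysis on Healing alone, while the primary endpoint is the union of Healed and Healing, so the numerator is not fixed

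*Combined protocol and SAP*

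**What the plan says.** Section 3.1, matched by the synopsis, sets the primary effectiveness endpoint as "Subject teeth in the Treatment Complete cohort that are healed or are healing at the twentyfour month Follow-up Visit". It then defines each term. The first is a state at follow-up: "Healed is defined by absence of a radiographic indication of apical periodontitis (PAI <3) and absence of clinical signs and symptoms". The second is a change from Baseline: "Healing is defined by a reduction of radiolucency (if radiolucency is present at Baseline) and/or reduction of clinical signs and symptoms", where the signs and symptoms also count only if they were present at Baseline.

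Section 13.4 specifies the primary analysis with only one of these terms: "The primary effectiveness analysis will be based on Healing at twenty-four (24) months for Treatment Complete Cohort". After naming Healing, with a capital letter, as the basis of the analysis, it gives the statistic: "The proportion of subjects with healing, along with the exact 95% confidence interval, will be provided for healing at 24 months". It does not mention Healed and does not cite 3.1.

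Section 13.1 sizes the study on a response rate, 85% against a literature value of 70%, and does not define response. Section 13.0 leaves details of method to the statistical analysis plan, but nothing in the supplied text settles which teeth count.

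**The concern.** The endpoint is a union of two defined categories, and the analysis section names one of them. Anyone programming 13.4 from the protocol's own definitions would count teeth that meet Healing and would not count a tooth that meets only Healed.

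Such teeth can be enrolled. Section 5.1 asks for a first or second molar indicated for root canal therapy and requires no lesion or symptom at Baseline. Section 7.4.4 lists asymptomatic irreversible pulpitis among the pulp diagnoses and normal apical tissue among the periradicular ones. A tooth like this that is sound at 24 months succeeds on the endpoint in 3.1 but could be scored a failure, or left unclassified, under 13.4.

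This is a single-arm study set against a fixed 70%, so the numerator decides the result. If the text leaves it open, the reading could be settled after the data are known.

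**Working it through.** **1. Inputs.** From 13.1: 86 evaluable subjects, null rate 70%, alternative 85%, two-sided binomial test at 5%, about 90% power, 108 enrolled with 20% loss. From 3.1: the two definitions. From 13.4: the analysed term. The documents give no split between Healed and Healing and no expected share of teeth free of disease at Baseline.

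**2. The plan's own figure.** Take the smallest r with P(X ≥ r | n = 86, p = 0.70) ≤ 0.025.
- r = 69, upper tail 0.0223. The lower tail is P(X ≤ 51) = 0.0224. Total two-sided alpha is 0.0447.
- Power = P(X ≥ 69 | 86, 0.85) = 0.914. The normal approximation gives 0.916.
- Enrolment: 86 / 0.80 = 107.5, rounded up to 108.

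The stated power of about 90% reproduces. The exact interval in 13.4 gives the same cut-off: 69/86 = 80.2% has an exact 95% CI of 70.2% to 88.0%, while 68/86 = 79.1% has a lower limit of 69.0%.

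**3. Which teeth differ between 3.1 and 13.4.**

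| Baseline | 24 months | Healed | Healing | In 3.1 union | In 13.4 read literally |
|---|---|---|---|---|---|
| Radiolucency, signs or symptoms | Fully resolved | Yes | Yes | Yes | Yes |
| Radiolucency, signs or symptoms | Reduced, not resolved | No | Yes | Yes | Yes |
| None of these | PAI below 3, no signs or symptoms | Yes | No: nothing to reduce | Yes | No |

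Only the third row separates the two. It takes Healing to require that a reduction has occurred. Section 3.1 does not say how a tooth with nothing present at Baseline is to be classed.

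**4. Size.** Let d be the share of all teeth in the third row, and hold the true composite rate at 85%. The analysed rate is 0.85 − d, and power is P(X ≥ 69 | 86, 0.85 − d). The two values of d are assumptions: 5% and 10% of responders, that is 0.05 × 85 = 4.25 and 0.10 × 85 = 8.5 percentage points.

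| d (points) | Teeth out of 86 | Analysed rate | Power |
|---|---|---|---|
| 0 (union) | 0 | 85% | 91.4% |
| 4.25 | 0.0425 × 86 = 3.7 | 80.75% | 61% |
| 8.5 | 0.085 × 86 = 7.3 | 76.5% | 25% |

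About four to seven teeth are enough to move the study from well powered to poorly powered.

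**The case against.** The best defence is that healing is the protocol's everyday word for the outcome. Section 3.0 says: "The purpose of this study is to assess healing rates and post-procedure pain following root canal therapy with the Sonendo GentleWave System", and the study title and the heading of 2.3 use the word in the same broad way. The union is stated twice, in the synopsis and in 3.1, so a report on any other numerator would contradict the declared endpoint. On this view 13.4 is shorthand and needs only a cross-reference. Much of that stands: the union is the likely intent, and the risk of a choice made after the data are seen is limited by the endpoint text.

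It does not remove the problem. Healing is also a defined term, 13.4 writes it with a capital, and the response in 13.1 does not resolve which sense applies.

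Two stronger readings are tempting and should not be drawn. The first is that Healing means incomplete healing only, so that 13.4 excludes every fully healed tooth and the analysed rate collapses. Section 3.1 does not say this. It asks for a reduction, and complete resolution is a reduction. The notion of incomplete healing comes from the literature background in 2.3: "Separating complete healing and incomplete healing will also more clearly present study results". That is a general remark on presentation, not a definition and not a rule that 13.4 breaks. The second is that 13.4 could be read as Healed only. It never uses that word, although 2.3 does favour a success definition close to it.

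**Conclusion.** The concern holds as a mismatch of terms between the endpoint and its analysis. Applied literally, 13.4 does not estimate the endpoint in 3.1, because it omits healed teeth with no radiolucency, signs or symptoms at Baseline. It does not omit healed teeth in general.

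The effect depends on the share of such teeth, which the documents do not give. With assumed shares of 4.25 and 8.5 points and a true composite rate of 85%, power falls from 91.4% to about 61% and 25%. If the union is analysed, the stated design applies unchanged. The point is about specification, and the documents do not show that a narrower numerator was intended.

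**What to change.** - In 13.4, state that the numerator is teeth Healed or Healing as defined in 3.1, in both sentences.
- In 13.1, use the same term for the response, so that the 85% and 70% refer to the same outcome.
- In 3.1 and the synopsis, make the categories mutually exclusive: a tooth that meets both definitions counts as Healed. Without this rule, separate rows would count some teeth twice.
- Report Healed and Healing separately beside the union, each with an exact 95% CI.

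The cost is a few sentences and one or two table rows. No sample size, alpha or power figure changes. The drawback for the sponsor is that the Healed-only rate cannot exceed the union and will look less favourable beside it. The change should be made before the 24-month data are analysed.

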## **13.5** Secondary Analysis

Secondary analysis will be completed after all Treatment Complete subjects complete the 24 month follow-up.

## 13.6 Safety Analyses

Incidence of device related adverse events as defined by perforation, instrument separation, root fracture, sodium hypochlorite accident or Gutta Percha extrusion, as related to the device will be summarized for the Safety Population.

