## 2.2.4 Perforation

Root perforations are shown to be one of the eminent causes of endodontic failures. They are artificial openings in root walls created by boring, piercing, or filing that result in a communication between the pulp space and periodontal tissues. These openings may cause secondary periodontal involvement and eventual loss of the tooth. latrogenic perforations are often due to insufficient attention to the details of internal anatomy and a failure to consider anatomic variations. They may also be due to lack of information on the canal anatomy and morphology, as the dental radiographs only provide a buccolingual view of the tooth. Accidental root perforations, which may have serious implications, occur in approximately 2–12% of endodontically treated teeth. Bacterial infection emanating either from the root canal or the periodontal tissues, or both, prevents healing and promotes inflammatory sequels where the supporting tissues have been exposed. This bacterial exposure may be followed by painful conditions, abscesses, and fistulae, including bone resorption processes. Once an infectious process has established itself at the perforation site, prognosis for treatment is precarious and the complication may prompt extraction of the affected tooth.

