## **13.0 STATISTICAL METHODS**

All required data for this study will be collected on paper or electronic Case Report Forms (CRFs). The Investigator (or designated study staff) will assure primary data collection based on source documented dental chart reviews. Independent monitoring will be performed to ensure that the investigator and his/her study team conducted the clinical investigation in accordance with contract specifications, study protocol, Declaration of Helsinki, and applicable local or national regulations, to ensure adequate protection of the rights and safety of subjects and the quality and integrity of the resulting data.

In general, quantitative variables will be summarized to indicate the population sample size (N), number of patients with available data (n), mean, standard deviation, median, minimum, and maximum values. Qualitative variables will be summarized by the population size (N), number of patients with available data (n), number of patients in each category, and the percentage of patients in each category. Analyses will be based on the Safety Population defined as all patients who receive the Sonendo GentleWave System procedure. Details of analysis methods will be described in the statistical analysis plan.

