## 13.1 Sample Size

All patients will receive root canal therapy with the Sonendo GentleWave System and will be subsequently followed for 24 months post procedure. A sample size of 108 subjects, assuming a 20% lost to follow-up or Treatment Incomplete Cohort rate, will result in approximately 86 subjects who would be evaluable for the primary efficacy endpoint. A sample size of 86 evauable subjects provides approximately 90% power to detect a difference between a 85% response rate for subjects using the Sonendo GentleWave System against a null hypothesis of a 70% response rate based on data presented in literature for traditional root canal therapy, using a two-sided binomial test at the 5% level of significance.

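### The primary safety endpoint is given no confidence interval in the supplied text, so even 0 events in about 108 subjects would be reported without its upper limit of about 3.4%

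*Combined protocol and SAP*

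**What the plan says.** The synopsis and section 3.2 name a primary safety endpoint: the incidence of perforation, instrument separation, root fracture, sodium hypochlorite accident or Gutta Percha extrusion, where related to the device. Its whole analysis is one sentence in section 13.6, under which the events "as related to the device will be summarized for the Safety Population".

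Section 13.0 states what a summary of a qualitative variable contains: the population size, the number with data, and the "number of patients in each category, and the percentage of patients in each category". It adds: "Details of analysis methods will be described in the statistical analysis plan". No separate, more detailed plan appears in the supplied text.

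The other primary endpoint is treated differently. Section 13.4 reports the healing proportion "along with the exact 95% confidence interval, will be provided for healing at 24 months", and section 13.1 supports it with a power statement. Safety has no interval, threshold, expected rate or precision statement.

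The population also differs between sections. The synopsis and section 3.2 restrict the safety endpoint to the Treatment Complete cohort. Section 13.6 uses the Safety Population, which section 13.2 defines as everyone who receives the procedure.

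**The concern.** This is a single-arm study with a narrow safety endpoint and roughly a hundred subjects. In that setting the upper confidence limit carries most of the information. A count of 0 (0%) tells the reader little until it is known which true rates the data rule out.

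The context makes a bare percentage easy to over-read. Sections 2.1 and 2.4 suggest that the device may reduce the risks of traditional therapy, and section 2.4 names instrument separation and perforation. Sections 2.2.4 and 2.2.6 then quote traditional rates for those two events, for example that perforations "occur in approximately 2–12% of endodontically treated teeth". A reader shown 0% will naturally set it beside those figures.

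**Working it through.** **The plan's own figure.** None is stated for safety. The effectiveness calculation in section 13.1 reproduces, so the sample sizes can be taken as given. Section 13.1 says that 86 evaluable subjects "provides approximately 90% power to detect a difference between a 85% response rate" "against a null hypothesis of a 70% response rate", "using a two-sided binomial test at the 5% level of significance". With n = 86, the smallest success count with an upper tail of at most 0.025 under 70% is 69 (tail 0.0223). The exact power at 85% is 0.914, in line with the stated 90%. For attrition, 108 × 0.80 = 86.4.

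**Which n applies to safety.** The 86 are those evaluable for healing at 24 months, after a 20% allowance for loss to follow-up or incomplete treatment. The Safety Population is everyone treated, so about 108. Section 5.0 caps enrolment at 120.

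**Exact (Clopper-Pearson) two-sided 95% limits.** For x = 0 the upper limit is 1 − 0.025^(1/n). For x > 0 it is the 97.5% quantile of Beta(x + 1, n − x).

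| Events | n = 108 |
|---|---|
| 0 | 0 to 3.36% |
| 1 | 0.02 to 5.05% |
| 2 | 0.23 to 6.53% |
| 3 | 0.58 to 7.90% |

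For zero events, n = 120 gives an upper limit of 3.03%.

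**What zero events in 108 would exclude.** A true rate p gives zero events with probability (1 − p)^108. It is excluded when that probability falls below 0.025.

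| Rate quoted in section 2.2 | P(0 events in 108) | Excluded by 0/108? |
|---|---|---|
| 1.0%, mean rotary instrument fracture | 0.338 | no |
| 1.6%, mean retained hand instruments | 0.175 | no |
| 2%, low end of perforation | 0.113 | no |
| 3.7%, top of rotary range | 0.017 | yes |
| 5%, discarded rotary instruments | 0.004 | yes |
| 7.4%, top of hand-instrument range | <0.001 | yes |
| 12%, top of perforation range | <0.001 | yes |

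A zero composite means zero events of each type, so 3.36% is also the upper limit for perforation and for instrument separation separately. With two events in the composite the limit of 6.53% no longer excludes 3.7% or 5%. The limit for any single component then depends on which events occurred, which is why the components need their own intervals.

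**Size needed.** For zero events to exclude 2%, n must be at least ln(0.025)/ln(0.98) = 182.6, so 183 subjects. That exceeds the maximum of 120.

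**Effect of the denominator.** If the Treatment Complete cohort of section 3.2 were used, and the whole 20% allowance were incomplete treatment, n could fall to 86. Zero events would then have an upper limit of 4.20%, and 3.7% would no longer be excluded (0.963^86 = 0.039). The numerator may change too. Section 7.10 lists root fracture, one of the five components, among the reasons for incomplete treatment. A subject stopped for that reason would leave the endpoint altogether.

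**The case against.** The strongest reply is that counts and percentages are ordinary safety reporting. Any reader given N and n can compute the exact limit, no decision rule depends on it, and section 13.0 leaves room for a later plan to add an interval. This stands in part. The supportable statement is that the supplied text specifies no interval, not that none will be calculated. But the endpoint is labelled primary, and the plan already commits to an exact interval for the other primary endpoint.

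Several stronger readings are tempting, and the documents do not support them:

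- A reader might infer that a zero count would be compatible with all the quoted complication rates. It would not: 0/108 excludes 3.7% and above.
- A reader might assume that a zero or near-zero count is likely. No expected device rate is stated. The narrow endpoint makes a low count plausible, but that is inference.
- A reader might use 86 as the safety denominator. That is the number evaluable for healing at 24 months, and it overstates the imprecision for the Safety Population.
- A reader might conclude that the other adverse events and SAEs collected under section 10 have no planned analysis. The general summary rule in section 13.0 can cover them. Specific tables are simply not listed.
- A reader might think that an upper limit below a quoted literature rate would justify a claim of fewer complications. It would not. Rates are quoted for only two of the five event types, in mixed units (teeth, instruments). The device treatment defined in section 10.5.1 starts at LuxaBite or Tooth Cap placement and ends at 100% completion. Shaping comes before it (section 7.5.4) and obturation after it (section 7.11). Perforation before enrolment is an intra-procedure exclusion (section 5.4), so that patient becomes a screen failure. Only device-related events count.

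Nor does the plan itself announce a safety comparison. The literature control concerns healing and post-procedure pain, and section 11.0 does not list fewer complications as a benefit.

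**Conclusion.** The concern holds as a gap in the specified analysis. Sections 13.0 and 13.6 provide only a count and percentage for a primary endpoint, while section 13.4 provides an exact interval for the other one. At about 108 treated subjects the missing information is an upper limit of 3.4% for zero events and 6.5% for two. Zero events leaves the quoted means of 1.0% and 1.6% and the 2% low end for perforation unexcluded, and excludes 3.7% and above.

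These figures assume one tooth per subject, independent subjects, and a Safety Population near the planned 108. The literature rates serve here only as yardsticks for precision, not as a benchmark that the device must meet. The point affects how the safety result is reported and read. It does not affect the validity of the effectiveness analysis or the sample size for it.

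**What to change.** In section 13.6:

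1. Report the number and percentage of subjects with at least one of the five device-related events, and with each event type separately, each with an exact (Clopper-Pearson) two-sided 95% confidence interval.
2. Base any statement about safety on the upper limit.
3. Use one denominator. Reconcile the Treatment Complete cohort in the synopsis and section 3.2 with the Safety Population in section 13.6, and say how events in subjects with incomplete treatment are counted.
4. State that the literature rates in section 2.2 are not a like-for-like comparator, and that no claim of fewer complications than traditional therapy will be made from this endpoint.

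The cost is a few table columns and a few sentences, with no new data. The downside for the sponsor is that a zero count will look less favourable beside its upper limit.

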## 7.10 Inability to Complete Treatment

If, for any reason, Sonendo GentleWave treatment cannot be completed over the course of no more than two visits, the subject will be considered as a Treatment Incomplete Subject. Subjects in the Treatment Incomplete Cohort will be documented as such but will not be followed for the study. No additional data will be collected on the Treatment Incomplete Cohort. Reasons for incomplete treatment may include, but are not limited to, periodontal issues, uncontrolled bleeding, root fracture, patient reported pain, etc.

These subjects will be counseled by the PI on any treatment they require. Subjects in the Treatment Incomplete Cohort will be responsible for any standard of care treatment.

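### Section 13.6 gives primary safety as one crude incidence with no time-at-risk rule and a disputed denominator, so any late device-related event is modestly understated

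*Combined protocol and SAP*

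**What the plan says.** The primary safety endpoint combines five device-related event types: root fracture, perforation, separated instruments, hypochlorite accidents and extruded gutta percha. Section 13.6 states that these "as related to the device will be summarized for the Safety Population". Sections 13.0 and 13.2 define that population as everyone who undergoes the GentleWave procedure, with no follow-up requirement. For qualitative variables, section 13.0 reports the population size, the number with data, then "number of patients in each category, and the percentage of patients in each category". It does not say which of the two counts is the percentage denominator.

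The visit schedule (section 8.0) assesses adverse events at the procedure, post-operatively and at 6, 12, 18 and 24 months. On subjects whose treatment cannot be finished, section 7.10 says: "No additional data will be collected on the Treatment Incomplete Cohort". Section 13.1 plans 108 subjects, "assuming a 20% lost to follow-up or Treatment Incomplete Cohort rate", which "will result in approximately 86 subjects who would be evaluable for the primary efficacy endpoint". The 20% is not divided between the two groups.

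Other sections give different rules for the same endpoint. The synopsis (study cohorts and primary safety endpoint) and section 3.2 restrict it to the Treatment Complete cohort. Section 13.7, which covers safety data as well as effectiveness data, states both last observation carried forward and complete-case analysis. No section plans person-time, a Kaplan-Meier estimate, or a split between procedural and later events.

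**The concern.** A crude incidence over all treated subjects suits events that arise during the procedure, when everyone is under observation. It does not suit events that can appear in the following two years. A Treatment Incomplete subject adds one to the denominator for the full 24 months but cannot add a late event to the numerator. A lost subject contributes only part of the time at risk. Under 13.6 as written, the more subjects fail to complete treatment or are lost, the lower the reported late incidence. The error runs in one direction, toward safety.

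The documents do not time the five event types. That root fracture could appear late is this review's reading. Section 7.10 lists root fracture as a reason for incomplete treatment, so some fractures would occur at the procedure.

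**Working it through.** **The plan's own figures.** 86 / 0.80 = 107.5, rounded up to 108; 108 × 0.80 = 86.4. An exact binomial test of 70% with n = 86 rejects at 69 or more responders (upper tail 0.0223, both tails 0.0447) and has power 0.914 at 85%. Section 13.1 reproduces. The plan gives no figure for safety incidence or its precision.

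**Inputs.** The combined rate of 20% and 108 subjects come from 13.1. The split of the 20%, the event timing and the loss timing are assumptions. So are equal risk in observed and unobserved subjects and no capture by remote contact.

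**Formula.** Let *a* be the Treatment Incomplete share, *b* the lost share, with *a* + *b* = 0.20, and *F* the mean fraction of 24-month late events that fall before loss. The observed share of late events is (1 − *a* − *b*) + *bF*, so with the Safety Population as denominator

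relative understatement = *a* + *b*(1 − *F*).

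| Split | Late-event timing | Loss timing | *F* | Understatement |
|---|---|---|---|---|
| *a* = 0.20 | any | none | – | 20.0% |
| *a* = 0.10, *b* = 0.10 | constant | uniform | 0.50 | 0.10 + 0.10 × 0.50 = 15.0% |
| *b* = 0.20 | rising linearly | uniform | 1/3 | 0.20 × 2/3 = 13.3% |
| *a* = 0.05, *b* = 0.15 | constant | uniform | 0.50 | 0.05 + 0.15 × 0.50 = 12.5% |
| *b* = 0.20 | constant | uniform | 0.50 | 0.20 × 0.50 = 10.0% |
| *b* = 0.20 | constant | all at 18 months | 0.75 | 0.20 × 0.25 = 5.0% |
| *b* = 0.20 | early (exponential, mean 6 months) | uniform | 0.769 | 0.20 × 0.231 = 4.6% |

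The working range is therefore about 5% to 20%. The lower end is not a strict floor: early events with all loss at 18 months would give 0.6%.

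**Treatment Complete denominator (synopsis, 3.2).** Relative understatement = [*b*/(1 − *a*)](1 − *F*). With constant hazard and uniform loss:
- all 20% incomplete: 0%
- 10% incomplete and 10% lost: (0.10 / 0.90) × 0.50 = 5.6%
- all 20% lost: 10.0%

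This choice removes the dilution from incomplete subjects but not from lost ones. It also discards procedural events in Treatment Incomplete subjects.

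**Missing-data rules (13.7).** Carrying forward a no-event status gives the same dilution. Complete case at 24 months avoids it, but could discard a subject who had an early event and then left.

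**Absolute size in 108 subjects.** The columns use 10% and 20% understatement.

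| Assumed true late incidence | Expected events | Reported incidence | Events missed |
|---|---|---|---|
| 2% | 2.16 | 1.8% to 1.6% | 0.2 to 0.4 |
| 5% | 5.40 | 4.5% to 4.0% | 0.5 to 1.1 |

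For comparison, 2/108 = 1.9% has an exact 95% confidence interval of 0.2% to 6.5%.

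**The case against.** The strongest reply is that the bias is not fixed by the plan, because the plan does not fix the denominator. Under the synopsis and section 3.2, Treatment Incomplete subjects leave the calculation. Under the complete-case sentence of 13.7, applied at 24 months, the dilution does not arise. This stands as a limit on the claim: no section says that an unobserved subject counts as event-free. It is not a defence of the plan, since the contradiction is itself a defect, and none of the stated rules handles both early and late events.

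A reader might infer that late events can never be seen in lost subjects. The documents do not support that. These subjects are observed until loss. Section 9.10 then calls for contact by mail, telephone or dentist, and section 7.19 includes adverse events in what is collected that way. The absence of later observation is complete only for Treatment Incomplete subjects.

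A reader might also take 86 as the corrected denominator. That is right only if the whole 20% contribute no time after the procedure. Under uniform loss, lost subjects contribute half the time at risk.

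Finally, a crude incidence over all treated subjects is a conventional safety summary, the expected counts are small, and section 13.0 defers analysis detail to the statistical analysis plan. These points stand and keep the severity low. No fuller safety-analysis text appears in the documents.

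**Conclusion.** The concern holds in a limited form. Under 13.6 as written, late device-related events are understated and no time-at-risk method is planned. The size is about 5% to 20% in relative terms, given the 20% combined rate, equal risk and no remote capture. In absolute terms it is about one event or less in 108 for an assumed late incidence of up to 5%, which is well inside the sampling uncertainty. A flat range of 10% to 20% is tempting. It needs constant hazard and losses no later on average than uniform over 24 months, and the documents give neither event nor drop-out timing.

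The conflict over the denominator needs no such assumptions: the synopsis and 3.2 name one population, 13.6 another, and 13.7 gives two incompatible missing-data rules. Severity is low, since the safety analysis is descriptive and has no hypothesis or performance goal.

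**What to change.** Reconcile the synopsis, 3.2, 13.6 and 13.7 to one rule for the primary safety endpoint, and split the report:

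- **Procedural events:** those during the procedure visit or visits, as a proportion of the full Safety Population, so that events in Treatment Incomplete subjects are kept.
- **Later events:** a 24-month Kaplan-Meier cumulative incidence, or events per person-year. Time runs from the procedure to the event or the last adverse-event assessment, whether visit or remote contact. Censor Treatment Incomplete subjects at their last procedure visit, and show the number observed at each visit.

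State that this censoring may be informative. Treatment Incomplete subjects did not receive the full device treatment, and section 7.10 gives root fracture, bleeding and pain among the reasons for stopping. In 13.7, remove either last observation carried forward or complete case for safety data.

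The cost is wording and one extra table, using onset dates that section 10.3 already collects. The reported late-event figure may be slightly less favourable.
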